3.4 Tertiary Endpoint

A series of variables that are among the most relevant for evaluation of safety were examined closely in our previous studies. In both groups we will continue to routinely monitor and record the same set of physiological variables in the proposed study, for a subset of data for a longer time period until after rewarming.

- Endpoint 1 – defined as *Mechanical ventilation and gas exchange parameters*
 - The following will be measured before (from start cooling), during and after Xenon administration (for 12h or until 12h after end of cooling hours pending which variable):
 - transcutaneous oxygen saturation
 - end-tidal carbon dioxide concentration
 - blood gas data
 - mechanical ventilation requirements (rate, peak inspiratory pressure, inspiratory time, PEEP settings)
 - FiO₂
 - average percentage Xenon in inspired gas mixture (when applicable)
 - tracheal tube cuff pressure.
- Endpoint 2 – defined as *Haemodynamic parameters*
 - The following will be measured before, during and after Xenon administration:
 - systolic, mean and diastolic arterial pressures; and heart rate variability
- Endpoint 3 – defined as *Inotropic drug requirements*
 - The following will be recorded before, during and after Xenon administration until 12h after end of cooling:
 - drug, dose and duration
- Endpoint 4 – defined as *Marker of myocardial impairment/insult*
 - The following will be recorded before and after Xenon administration:
 - plasma levels Troponin T (marker of myocardial cell death) recorded before and after Xenon administration until 12h after end of cooling:
- Endpoint 5 – defined as timecourse and peak value of *Markers of hepatic impairment*
 - The following will be recorded before and after Xenon administration until 12h after end of cooling:
 - alanine aminotransferase, alkaline phosphatase and lactate dehydrogenase
- Endpoint 6 – defined as timecourse and peak value of *Markers of renal impairment*

Neonatal Xenon Breathing Device: CoolXenon3 Study	Protocol	CI/2013/4414
	Version	Issue 2, Revision 3
	Issue Date	18 Sept 2019
	Page	22 of 79

- The following will be recorded before, during and after Xenon administration until 12h after end of cooling:
 - oliguria - defined as urine output < 1 ml/kg/h - from age > 24h
 - raised creatinine > 100 at > 24h of age.
- Endpoint 7 – defined as *Evidence of infection*
 - The following will be recorded:
 - culture proven
 - need for antibiotics for 5 or more days
 - raised CRP occurring within 24h or later.
- Endpoint 8 – defined as *Length of hospital stay including duration of stay in local hospital after discharge from St Michaels hospital*
 - This will be recorded
- Endpoint 9 – defined as *age when full oral feeding was achieved by breast or bottle or tube*
 - This will be recorded
- Endpoint 10 – defined as *Haematology measurements*
 - The following will be recorded before and after Xenon administration (routinely recorded 24 hrly):
 - Coagulopathy - INR > 2 and/or APTT > 50
 - FBC
- Endpoint 11 – defined as *Serum chemistry measurements*
 - The following will be recorded before and after Xenon administration
 - serum sodium, potassium, chloride, magnesium, phosphate, calcium, (urea, creatinine as above), glucose, (liver enzymes as above), bilirubin, albumin
 - drug levels may be analysed on clinical indication (Gentamicin levels, Phenobarbital levels)
- Endpoint 12 – defined as aEEG background pattern and *Evidence of seizures*
 - The following will be recorded before, during and after Xenon administration until 12h after end of cooling:
 - evidence from continuous aEEG/EEG recording
 - any anticonvulsant treatments given.

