At the end of the prescribed period of Xe delivery the tracheal tube would be reconnected directly to the mechanical ventilator and normal ventilation and gas mixtures set as clinically appropriate. The cuff of the tracheal tube would be deflated. This tracheal tube would be replaced with an uncuffed tube at a later timepoint as clinically indicated or kept until the patient was extubated after rewarming. Cooling regimes last for 72hrs before slow rewarming commences (0.1-0.4°C per hour). The standard cooling protocol would continue for many more hours after cessation of the additional Xenon regime.

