4.9 Follow Up

4.9.1 Short term information and investigations (*before discharge from hospital*)

These are part of routine clinical practice.

1. Survival
2. Duration of hospitalisation
3. Time to full oral feeds, breast or bottle or tube
4. Hypoxic-ischaemic or other injury² and MRI biomarkers such as absolute NAA quantification in Thalamus and white matter fractional anisotropy using tract based spatial statistics⁴ on MRI scan, which includes Magnetic Resonance Spectroscopy, undertaken around 48 hours and around day7 of life.
5. Intracranial or intraventricular haemorrhage (on MRI, CT or ultrasound)
6. Major venous thrombosis (on MRI or ultrasound)
7. Resistance Index (Doppler examination of cerebral blood flow velocities)
8. Amplitude integrated EEG (aEEG) continuously recorded until after rewarming. Assessment of time to normalisation of background activity, seizure occurrence and duration
9. Pulmonary hypertension needing treatment
10. Pulmonary haemorrhage
11. Pneumonia
12. Pulmonary air leak
13. Systemic hypotension needing inotropic support
14. Prolonged blood coagulation time assessed before Xenon and at ~24 hours and/or at clinically indicated timepoints
15. Cardiac arrhythmia (not temperature induced low Heart Rate)
16. Thrombocytopenia (platelets <100,000/uL)
17. Culture proven sepsis
18. Necrotising enterocolitis, medical, radiological or surgically proven
19. Plasma markers of global (increased lactate dehydrogenase (LDH)) or cardiac compromise (increased cardiac Troponin T (cTnT))
20. Renal failure treated with dialysis

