8.5.4 Patient Follow-up

8.5.4.1 Short term information and investigations (*before discharge from hospital*):

These are part of routine clinical practice.

1. Survival
2. Duration of hospitalisation
3. Time to full oral feeds, breast, bottle or tube.
4. Hypoxic-ischaemic or other injury² and MRI biomarkers including quantification of NAA in thalamus and fractional anisotropy in white matter using tract based spatial statistics⁴ on MRI scan, which includes Magnetic resonance spectroscopy, undertaken around 48 hours of life and around day 7 of life.
5. Intracranial or intraventricular haemorrhage (on MRI, CT or ultrasound)
6. Major venous thrombosis (on MRI or ultrasound)
7. Resistance Index (Doppler examination of cerebral blood flow velocities)
8. Amplitude integrated EEG (aEEG) continuously recorded until after rewarming, or 82h in cooled-only infants. Assessment of time to normalisation of background activity, seizure occurrence and duration

Neonatal Xenon Breathing Device: CoolXenon3 Study	Protocol	CI/2013/4414
	Version	Issue 2, Revision 3
	Issue Date	18 Sept 2019
	Page	41 of 79

9. Pulmonary hypertension needing treatment
10. Pulmonary haemorrhage
11. Pneumonia
12. Pulmonary air leak
13. Systemic hypotension needing inotropic support
14. Prolonged blood coagulation time assessed before Xenon and at ~24 hours and/or at clinically indicated timepoints
15. Cardiac arrhythmia (not temperature induced low Heart Rate)
16. Thrombocytopenia (platelets <100,000/ul)
17. Culture proven sepsis
18. Necrotising enterocolitis or intestinal perforation, medical, radiological or surgically proven
19. Plasma markers of global (increased lactate dehydrogenase (LDH)) or cardiac compromise (increased cardiac Troponin T (cTnT)) or plasma lactate
20. Renal failure treated with dialysis

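### The end of aEEG recording is stated three ways, one of them different by arm, and Endpoints 2, 11 and largely 10 are timed only by Xenon administration

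*Protocol*

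**What the plan says.** Three places in the protocol state when aEEG recording stops.

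- Section 8.5.4.1, item 8: aEEG is "continuously recorded until after rewarming, or 82h in cooled-only infants".
- Section 4.9.1, item 8, in an otherwise nearly identical list: "Amplitude integrated EEG (aEEG) continuously recorded until after rewarming", with no distinction between arms.
- Section 3.4, Endpoint 12 (aEEG background and seizures): "The following will be recorded before, during and after Xenon administration until 12h after end of cooling".

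Section 4.6.1 gives the cooling timetable: "Cooling regimes last for 72hrs before slow rewarming commences", at 0.1-0.4 °C per hour.

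On the safety variables, 3.4 opens with "In both groups we will continue to routinely monitor and record the same set of physiological variables in the proposed study". It then times nine of its twelve endpoints (1-6 and 10-12) by reference to Xenon. For Endpoint 2, haemodynamics, the whole timing statement is "The following will be measured before, during and after Xenon administration". Endpoint 11, serum chemistry, is recorded before and after Xenon with no other time reference. Endpoint 10, haematology, is worded the same way and adds only that recording is routinely 24-hourly.

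**The concern.** Time to recovery of a normal aEEG is the first secondary endpoint in 3.3, and seizures belong to Endpoint 12. Both depend on how long the trace is watched. An infant whose trace has not recovered when recording stops is censored at that point, and a seizure after that point is not seen on aEEG. If the stopping rule depends on the arm, a difference in either measure can arise with no treatment effect. The protocol itself gives reason for care here: sections 1.0 and 2.3 say that Xenon suppresses the trace during delivery and for a short time afterwards, and that seizures could occur when it was stopped very fast. Section 10.1 plans descriptive comparisons between the arms and with 45 historical cooled-only infants, and such comparisons are only as good as the match in observation periods.

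The second part is smaller. Control infants never receive Xenon (5.7), so an instruction timed only by Xenon does not tell staff when to record them. Where that is the only time reference, the two groups may be measured at different ages.

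**Working it through.** **1. Inputs.** Cooling lasts 72 h and rewarming runs at 0.1-0.4 °C/h (4.6.1). The target temperature is 33.5 °C (3.2). Cooling starts by 3 h of age (4.3). The control-arm limit is 82 h (8.5.4.1), with no statement of whether it counts from birth or from start of cooling. The protocol does not define normal temperature in figures; 36.5-37.0 °C is assumed.

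**2. The 82 h figure.** The protocol gives no derivation. It equals 72 + 10 h. Rewarming in 10 h needs (36.5 - 33.5)/10 = 0.30 °C/h or (37.0 - 33.5)/10 = 0.35 °C/h. So 82 h matches the end of rewarming only for rates of about 0.30-0.35 °C/h, a narrow part of the permitted range.

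**3. End of rewarming**, in hours from start of cooling = 72 + (normal temperature - 33.5)/rate.

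| Assumed normal temperature | Rate (°C/h) | Rewarming (h) | End (h) | Difference from 82 h |
|---|---|---|---|---|
| 36.5 °C | 0.4 | 3.0/0.4 = 7.5 | 79.5 | -2.5 |
| 36.5 °C | 0.1 | 3.0/0.1 = 30 | 102 | +20 |
| 37.0 °C | 0.4 | 3.5/0.4 = 8.75 | 80.75 | -1.25 |
| 37.0 °C | 0.1 | 3.5/0.1 = 35 | 107 | +25 |

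With 82 h counted from start of cooling, the Xenon arm is recorded from 2.5 h less to 25 h more than controls. The upper extreme is 25/82 = 30% longer.

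**4. If 82 h is counted from birth.** With cooling started at age 0-3 h, 82 h of age falls 79-82 h after cooling starts. The difference then runs from 79.5 - 82 = -2.5 h to 107 - 79 = +28 h. The choice of origin moves the upper end by 3 h.

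**5. Against Endpoint 12.** Taking the end of cooling as 72 h, the limit is 72 + 12 = 84 h from start of cooling, or 84-87 h of age. The 82 h limit stops 2 h short of this if counted from start of cooling, and 2-5 h short if counted from birth. A control infant handled under 8.5.4.1 would therefore not have the full recording that Endpoint 12 asks for.

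**6. Time references in 3.4, side by side.**

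| Endpoint | Time reference other than Xenon |
|---|---|
| 1 | Start of cooling; for some variables, also 12 h after end of cooling |
| 3, 4, 5, 6, 12 | 12 h after end of cooling |
| 10 | Routinely 24-hourly, no stated end |
| 2, 11 | None |
| 7, 8, 9 | Not tied to Xenon |

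Only Endpoints 2 and 11, and largely 10, lack a usable reference for controls. Sections 8.5.3 and Appendix A1 do not supply one: they place data collection, including blood count and serum chemistry in Appendix A1, before and after Xenon, and the only other time named is after cooling in 8.5.3.

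**The case against.** The strongest reply is that arm-neutral clocks already exist for most of this. A reader might infer that controls have no observation windows for any safety variable. The documents do not support that. Endpoints 3-6 and 12 share a cooling-based outer limit, and Endpoint 1 is worded "The following will be measured before (from start cooling), during and after Xenon administration (for 12h or until 12h after end of cooling hours" for at least some variables. What controls lack there is only the split into before, during and after. For variables recorded continuously or at routine intervals, an analysis plan that is not shown could map that split onto a matched period. This stands, and the point is narrowed accordingly.

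A reader might also infer bias in peak enzymes or inotrope need. That is not supported either. Peak LDH is fixed within 72 h of life (3.3), the other liver markers run to 12 h after the end of cooling, and inotropes are counted over the neonatal unit stay in both arms (4.9.2, 8.5.4.2).

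Third, 82 h may be meant only as an approximate end of rewarming, so that recording lengths would often be similar. That is plausible at 0.30-0.35 °C/h, but the text does not say so and gives the figure for one arm only.

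Fourth, 25 h extra in the Xenon arm might be read as the expected imbalance. It is the extreme of a two-sided range, and nothing in the protocol shows how many infants recover their trace or have seizures after 82 h. The size of any bias is therefore unknown.

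The introduction to 3.4 does extend an unnamed subset of the data until after rewarming in both groups. Because the subset is not named, this does not settle the timing of Endpoints 2, 10 or 11. An analysis plan also cannot restore an aEEG trace after recording has stopped, or decide which of three protocol instructions staff followed.

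**Conclusion.** The concern holds in this form. Sections 8.5.4.1, 4.9.1 and 3.4 give three different ends for the same aEEG recording, and 8.5.4.1 sets a different stopping rule by arm. Followed as written, it could leave the Xenon arm recorded from about 2.5 h less to 25 h more than controls. That range assumes a normal temperature of 36.5-37.0 °C, 72 h of cooling and 82 h counted from start of cooling; counting from birth raises the upper end to 28 h. It measures possible unequal observation, not bias itself, and the comparisons exposed are seizures and time to normal aEEG. In addition, Endpoints 2 and 11, and largely 10, have no usable time reference in controls although both groups are to be recorded. The primary Bayley comparison at 18 months is not affected.

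**What to change.** - In 8.5.4.1, remove the 82 h that applies only to cooled-only infants. State one end of aEEG recording and one time origin for both arms, and use the same words in 4.9.1 and Endpoint 12. The limit of 12 h after the end of cooling already in Endpoint 12 would serve, provided the end of cooling is defined (end of the 72 h, or end of rewarming). Any single rule applied to both arms removes the problem.
- In 3.4, for Endpoints 2, 10 and 11, give control infants a reference period matched to the 18 h of Xenon, on the same clock in both arms (hours from start of cooling or from randomisation). Carry it into 8.5.3 and Appendix A1.

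The cost is wording in a few sections and slightly longer recording in some infants: under the Endpoint 12 limit taken as 84 h, 2 h more for controls if 82 h counts from start of cooling, and 2-5 h more if it counts from birth. If that limit is chosen, infants rewarmed more slowly than 3.0/12 = 0.25 to 3.5/12 = 0.29 °C/h reach it before rewarming ends. Any later trace should then be left out of the between-arm comparison or obtained in both arms alike. These changes concern data collection only, not treatment.

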4.0 Study Design

This is a prospective randomised comparative clinical outcome study conducted in St Michael's Hospital, Bristol and Hammersmith Hospital, London.

4.1 Study design and procedures

Infants will be eligible for Xenon if the St Michael's hospital standard inclusion criteria for cooling are met and additional inclusion criteria for Xenon administration are met.

4.1.1 St Michael's hospital standard inclusion criteria for cooling

Standard Hypothermia Treatment Criteria for 72 hrs of cooling — all of criteria A, B and C.

A: *Infants ≥ 36.0 weeks gestation (estimated or clinical assessment) with at least ONE of the following:*

- i. Apgar score of ≤5 at ten (10) minutes after birth
- ii. Continued need for resuscitation, including tracheal or mask ventilation, at ten minutes after birth
- iii. Acidosis defined as either umbilical cord pH or any arterial, venous or capillary pH within 60 minutes of birth less < 7.00
- iv. Base deficit ≥16 mmol/L in umbilical cord blood sample or any blood sample within 60 minutes of birth (arterial or venous blood). If the infant meets criterion A then assess for neurological abnormality using criterion B and C (by trained personnel):

B: *Moderate or severe encephalopathy as evidenced by any of the following:*

Neonatal Xenon Breathing Device: CoolXenon3 Study	Protocol	CI/2013/4414
	Version	Issue 2, Revision 3
	Issue Date	18 Sept 2019
	Page	23 of 79

- i. Altered state of consciousness (reduced or absent responses or pathological irritability and hyper responsive and at least ONE or more of the following:
 - ii. Hypotonia
 - iii. Abnormal reflexes including oculomotor or pupillary abnormalities
 - iv. Absent or weak suck
 - v. Clinical seizures, as recorded by trained personnel

AND

C: At least 30 minutes duration of amplitude-integrated electroencephalography (aEEG) recording that shows abnormal background aEEG activity. The decision to cool is based on the worst 30 min section of the aEEG, not the best³⁸ or seizures (clinical or electrical) thus meeting ONE of the following:

- i. Normal background with some (> 5 min) electrical seizure activity
- ii. Moderately abnormal activity (upper margin of trace >10µV and lower margin <5µV)
- iii. Suppressed activity (upper margin of trace <10µV and lower margin of trace <5µV)
- iv. Definite seizure activity

4.1.2 Exclusion criteria for cooling in the CoolXenon3 study

- a. Infants expected to be greater than 3 hours of age at the time of starting cooling treatment.
- b. Futility. Where prognosis is considered to be hopeless e.g. no cardiac output for 20 minutes.

4.1.3 Additional inclusion criteria for Xenon

Before being considered for additional inhaled Xenon therapy via the breathing gas mixture, the infant would need to meet further additional entry criteria (all must be met):

- i. Intubated, ventilated, sedated, being cooled.
- ii. ≤5 hours old
- iii. Any seizures under control.
- iv. Weight > 2nd centile for gestational age
- v. Stable cardiovascular parameters; Mean arterial pressure >40mmHg.
- vi. Oxygen requirement via mechanical ventilator < 40%.
- vii. Positive End Expiratory Pressure (PEEP) requirement ≤ 8cm H₂O
- viii. Arterial/capillary/venous pCO₂ < 7.0kPa (ideally arterial). Venous can be higher if peri-arrest and tissues have been very recently Ischaemic
- ix. Postnatal age ≤ 5 hours
- x. Absence of major congenital abnormalities, imperforate anus and in particular any bowel obstruction, congenital abnormalities suggestive of chromosomal anomaly or other syndromes that include brain dysgenesis. Congenital syndromes affecting the brain should be excluded when diagnosed.

4.2 Consent

Informed written consent will be obtained from a parent (only the mother can consent if parents are not married) after a full verbal and written explanation of the study by a named physician or trained nurse like an advanced nurse practitioner. Such staff will also meet with parents during the intervention period to ensure that they understand the study procedures and continue to consent to participate in the study. Information can be given by local trained staff and consent can also be taken over the phone with the mother if she is unable to be available for the consent process (e.g. cannot be moved shortly after Caesarean Section).

Approval for the study is being obtained from the Regional South West Research Ethics Committee covering St Michael's Hospital.

Most of the patients (61%) will be born outside the study hospital (Outborn) and brought to the hospital by a dedicated retrieval team and ambulance.

The local delivery hospitals will have medical staff (e.g. consultants, specialist registrars, advanced nurse practitioners) trained in consenting for the CoolXenon3 trial. A training log with signatures, a short CV and competency approval will be kept centrally.

Neonatal Xenon Breathing Device: CoolXenon3 Study	Protocol	CI/2013/4414
	Version	Issue 2, Revision 3
	Issue Date	18 Sept 2019
	Page	24 of 79

Parents will receive a written information leaflet (1 page, short version) when the infant is eligible for cooling treatment. Staff will discuss CoolXenon3 with parents as soon as practically possible. Parents will be able to speak on the phone to a member of the treatment team if they need further information and help with the consent process. Parents will also be offered the opportunity to speak to members of the treatment team that are picking up the baby for transport.

Trained staff on the transport team can take consent for the study.

A more detailed information sheet regarding the trial will be given to parents after the first conversation or at the earliest suitable time.

4.2.1 Which of the parents can consent to letting the child enter the trial?

- Either parent if they are married.
- If the parents are not married, only the mother can consent - provided she is awake and understanding (e.g. not under the influence of anaesthetic drugs)

If the mother is not in a state to understand the situation and the biological father does currently not have legal parental responsibility he can assent for the trial until the mother is awake/understanding the child's condition and able to decide on consent.

A parent who is eligible to consent can, at any time and without a specific reason, withdraw the child from the study. In this situation, Xenon treatment will then be stopped as soon as possible and medically safe (within minutes).

4.3 Randomisation

The babies entered into the study will be randomised into two groups on a 1:1 basis. Randomisation will be via sealed opaque envelopes containing details of treatment allocation and [an] identifying adhesive label(s) to be attached to the CRF binder. Neonates meeting all the entry criteria can be included. In this study early randomisation before 5h of age is paramount. The maximum target delay before starting cooling is before 3h of age and for Xenon this value is 5h of age. These are maximum delay values however, so consent and randomisation need to take place as early as possible.

4.4 Clinical management

The neonates would be sedated, mechanically ventilated and cooled according to the protocol for cooling listed above, as this is standard treatment. In the case of retrieved babies, cooling is always started before transfer to Bristol (active or passive cooling). If not before, active cooling starts when the transport team arrives. Antibiotics, fluid management and sedative drugs used would be unmodified.

Neonates would be entered into the study according to the set criteria within a maximum of 5hrs of birth with respect to adding Xenon to the existing underlying standard cooling regime which has started within 3 hrs (passive or active).

